10. PROPOSED TABLES, LISTINGS, AND FIGURES

Summary Tables

Accountabili	ty and Baseline Characteristics
14.1.1	Subject Disposition (All Subjects Enrolled)
14.1.2.1	Demographics and Baseline Characteristics (All Subjects Enrolled)
14.1.2.2	Dry Eye Assessments at Screening (All Subjects Enrolled)
14.1.3	Study Drug Exposure (All Subjects Treated)
14.1.4.1	Concomitant Medications for Double-Masked Period by Generic Name and Drug
	Classification (Safety Population)
14.1.4.2	Concomitant Medications for Placebo Run-in Period by Generic Name and Drug
	Classification (Run-in Population)
Efficacy (all a	analyses on mITT population)
14.2.1.1	Summary of SANDE Questionnaire Part 1 Global Symptom Score
14.2.2.1.1	Summary of SPEED Questionnaire Total Symptom Score
14.2.2.2	Summary of SPEED Questionnaire Type of Symptom Experience and When
	Symptoms Occur
14.2.3.1.1	Summary of 7-item Symptom Questionnaire Score – Eye Dryness
14.2.3.2.1	Summary of 7-item Symptom Questionnaire Score – Burning/Stinging
14.2.3.3.1	Summary of 7-item Symptom Questionnaire Score – Photophobia
14.2.3.4.1	Summary of 7-item Symptom Questionnaire Score – Foreign Body Sensation
14.2.3.5.1	Summary of 7-item Symptom Questionnaire Score – Blurred Vision
14.2.3.6.1	Summary of 7-item Symptom Questionnaire Score – Itching
14.2.3.7.1	Summary of 7-item Symptom Questionnaire Score – Pain
14.2.4.1.1	Summary of Staining of the Lid Wiper Area – Study Eye
14.2.4.2	Summary of Staining of the Lid Wiper Area – All Qualifying Eyes
14.2.4.3	Summary of Fluorescein Score – Study Eye
14.2.4.4	Summary of Fluorescein Score – All Qualifying Eyes
14.2.4.5	Summary of Lissamine Score – Study Eye
14.2.4.6	Summary of Lissamine Score – All Qualifying Eyes
14.2.5.1.1	Summary of Bulbar Conjunctival Staining Total Score – Study Eye
14.2.5.2	Summary of Bulbar Conjunctival Staining Total Score – All Qualifying Eyes
14.2.5.3	Summary of Bulbar Conjunctival Inferior Nasal Region Score – Study Eye
14.2.5.4	Summary of Bulbar Conjunctival Inferior Nasal Region Score - All
	Qualifying Eyes
14.2.6.1.1	Summary of Corneal Staining Total Score – Study Eye
14.2.6.2	Summary of Corneal Staining Total Score – All Qualifying Eyes
14.2.6.3	Summary of Corneal Staining Inferior Region Score – Study Eye
14.2.6.4	Summary of Corneal Staining Inferior Region Score – All Qualifying Eyes
14.2.7.1.1	Summary of Tear Breakup Time (TBUT) – Study Eye
14.2.7.2	Summary of Tear Breakup Time (TBUT) – All Qualifying Eyes
14.2.8.1	Summary of SANDE Part 2 Symptom Frequency Score
14 2 8 2	Summary of SANDE Part 2 Symptom Severity Score

14.2.9.1	Summary of SANDE Questionnaire Part 1 Symptom Frequency Score
14.2.9.2	Summary of SANDE Questionnaire Part 1 Symptom Severity Score
14.2.10.1	Proportion of Subjects with at Least a 20% Improvement from Baseline in the
	SANDE Part 1 Global Symptom Score
14.2.10.2	Proportion of Subjects with at Least a 20% Improvement from Baseline in the
	SANDE Part 1 Symptom Frequency Score
14.2.10.3	Proportion of Subjects with at Least a 20% Improvement from Baseline in the
	SANDE Part 1 Symptom Severity Score
14.2.11.1	Proportion of Subjects with at Least a 10% Improvement from Previous Visit in
	the SANDE Part 2 Symptom Frequency Score
14.2.11.2	Proportion of Subjects with at Least a 10% Improvement from Previous Visit in
	the SANDE Part 2 Symptom Severity Score
	3 1
Exploratory	(all analyses on mITT population)
14.2.12.1	Summary of Expression of the COX-2 Gene in the Lid Wiper
14.2.12.2	Summary of Expression of the Cytokeratin10 Gene in the Lid Wiper
14.2.12.3	Summary of Expression of the HLA-DR Gene in the Lid Wiper
14.2.12.4	Summary of Expression of the IFN-γ Gene in the Lid Wiper
14.2.12.5	Summary of Expression of the IL-1β Gene in the Lid Wiper
14.2.12.6	Summary of Expression of the IL-8 Gene in the Lid Wiper
14.2.13.1	Summary of Expression of the COX-2 Gene in the Bulbar Conjunctiva
14.2.13.2	Summary of Expression of the Cytokeratin 10 Gene in the Bulbar Conjunctiva
14.2.13.3	Summary of Expression of the HLA-DR Gene in the Bulbar Conjunctiva
14.2.13.4	Summary of Expression of the IFN-γ Gene in the Bulbar Conjunctiva
14.2.13.5	Summary of Expression of the IL-1β Gene in the Bulbar Conjunctiva
14.2.13.6	Summary of Expression of the IL-8 Gene in the Bulbar Conjunctiva
14.2.14	Summary of MMP-9 Activity in Tears
14.2.15	Summary of Prostaglandin Levels in Tears
14.2.16	Pearson Correlations Between Responses and Baseline scores for tear osmolarity,
	Meibomian gland assessment and the Schirmer test
Safety	
14.3.1.1.1	Summary of Treatment-emergent Adverse Events – Double Masked Period (Safety
	Population)
14.3.1.1.2	Summary of Treatment-emergent Adverse Events – Placebo Run-in Period (Run-in
	Population)
14.3.1.2.1	Treatment-emergent Adverse Events by System Organ Classification, Preferred
	Term, and Greatest Severity – Double Masked Period (Safety Population)
14.3.1.2.2	Treatment-emergent Adverse Events by System Organ Classification, Preferred
	Term, and Greatest Severity – Placebo Run-in Period (Run-in Population)
14.3.1.3.1	Adverse Events Related to Study Drug by System Organ Classification and
	Preferred Term – Double Masked Period (Safety Population)
14.3.1.3.2	Adverse Events Related to Study Drug by System Organ Classification and
	Preferred Term - Placebo Run in Period (Run in Population)

14.3.1.4.1	Treatment-emergent Serious Adverse Events by System Organ Classification and
14.3.1.4.2	Preferred Term - Double Masked Period (Safety Population) Treatment-emergent Serious Adverse Events by System Organ Classification and Preferred Term – Placebo Run-in Period (Run-in Population)
14.3.1.5.1	Treatment-emergent Adverse Events Leading to the Discontinuation of Study
	Drug by System Organ Classification and Preferred Term - Double Masked Period
14.3.1.5.2	(Safety Population) Treatment-emergent Adverse Events Leading to the Discontinuation of Study Drug by System Organ Classification and Preferred Term - Placebo Run-in Period
	(Safety Population)
14.3.4.1	Chemistry Laboratory Values by Study Visit (Safety Population)
14.3.4.2	Hematology Laboratory Values by Study Visit (Safety Population)
14.3.5.1	Summary of Best Corrected Visual Acuity (BCVA) by Study Visit (Safety
14252	Population)
14.3.5.2	Summary of Best Corrected Visual Acuity (BCVA) by Study Visit (Run-in
14261	Population) Superson of Vital Signs by Study Visit (Safety Pagellation)
14.3.6.1	Summary of Vital Signs by Study Visit (Safety Population)
14.3.6.2	Summary of Vital Signs by Study Visit (Run-in Population)
14.3.7.x.1	Summary of Biomicroscopy and Eye Examination Data (Safety Population)
14.3.7.x.2	Summary of Biomicroscopy and Eye Examination Data (Safety Population)
	• Lashes
	• Eyelid Erythema
	• Eyelid Edema
	Conjunctival Erythema
	Conjunctival Edema
	• Tear Film Debris
	 Corneal Endothelial Changes
	Corneal Edema
	Anterior Chamber Cells
	Anterior Chamber Flare
	• Lens pathology
14.3.8.1	Summary of Drop Instillation Discomfort by Study Visit (Safety Population)
14.3.8.2	Summary of Drop Instillation Discomfort by Study Visit (Run-in Population)
	Data Listings
16.2.1.1	Data Listings Study Completion
16.2.1.2	Randomization Criteria
16.2.2.1	Protocol Deviations/Violations
16.2.2.2	Inclusion/Exclusion Criteria
16.2.3	Study Populations
16.2.4.1	Demographics

16.2.4.2.1	Ocular Medical History
16.2.4.2.2	Medical History
16.2.4.3	Prior and Concomitant Medications
16.2.5.	Study Drug Administration and Accountability
16.2.6.1.1	SANDE Questionnaire Part 1
16.2.6.1.2	SANDE Questionnaire Part 2
16.2.6.1.3	SPEED Questionnaire
16.2.6.1.4	7-item Symptom Questionnaire Score
16.2.6.1.5	Staining of the Lid Wiper Area
16.2.6.1.6	Bulbar Conjunctival Staining Total Score
16.2.6.1.7	Corneal Staining Total Score
16.2.6.2.1	Tear Osmolarity
16.2.6.2.2	Meibomian Glands
16.2.6.2.3	Schirmer's Test
16.2.6.2.4	Intraocular Pressure
16.2.6.3.1	Tear Breakup Time (TBUT)
16.2.6.3.2	Expression of the COX-2, Cytokeratins, HLA-DR, IFN-γ, IL-1β, IL-8 Genes in the Lid Wiper
16.2.6.3.3	Expression of the COX-2, Cytokeratins, HLA-DR, IFN-γ, IL-1β, IL-8 Genes in the Bulbar Conjunctiva
16.2.6.3.4	MMP-9 Activity in Tears
16.2.6.3.5	Prostaglandin Levels in Tears
16.2.7.1	Adverse Events
16.2.7.2	Adverse Events Leading to Discontinuation
16.2.8.1.1	Chemistry Laboratory Tests
16.2.8.1.2	Hematology Laboratory Tests
16.2.8.1.3	Urine Pregnancy Tests
16.2.8.2	Best Corrected Visual Acuity (BCVA)
16.2.8.3	Vital Signs
16.2.8.4	Biomicroscopy and Eye Examination
16.2.8.5	Abnormal Physical Examinations
16.2.9	Drop Instillation Discomfort
16.2.10	Phone Call
	Figures
14.2.1.2	Summary of SANDE Questionnaire Part 1 Global Symptom Score
14.2.2.1.2	Summary of SPEED Questionnaire Total Symptom Score
14.2.3.1.2	Summary of 7-item Symptom Questionnaire Score – Eye Dryness
14.2.3.2.2	Summary of 7-item Symptom Questionnaire Score – Burning/Stinging
14.2.3.3.2	Summary of 7-item Symptom Questionnaire Score – Photophobia
14.2.3.4.2	Summary of 7-item Symptom Questionnaire Score – Foreign Body Sensation
14.2.3.5.2	Summary of 7-item Symptom Questionnaire Score – Blurred Vision
14.2.3.6.2	Summary of 7-item Symptom Questionnaire Score – Itching
14.2.3.7.2	Summary of 7-item Symptom Questionnaire Score – Pain

14.2.4.1.2	Summary of Staining of the Lid Wiper Area – Study Eye
14.2.5.1.2	Summary of Bulbar Conjunctival Staining Total Score – Study Eye
14.2.6.1.2	Summary of Corneal Staining Total Score – Study Eye
14.2.7.1.2	Summary of Tear Breakup Time (TBUT) – Study Eye

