1.1. STUDY OVERVIEW

This is a multi-center, randomized, double-masked, placebo-controlled, parallel group Phase 2b trial designed to evaluate symptoms and signs in subjects with mild to moderate dry eye disease. It is anticipated that approximately 125 subjects with dry eye will need to be screened in order to randomize about 65 subjects and complete approximately 60 subjects. Subjects who meet inclusion/exclusion criteria will be enrolled in a single-masked placebo run-in period for up to 14 days. At the end of the run-in period, eligible subjects will be randomly assigned in a double-masked fashion to receive either 0.017% P-321 Ophthalmic Solution or Placebo TID for 28 days. The study will consist of four study visits and a follow up phone call: Visit 1 (Screening Visit), Visit 2 (Randomization and Treatment Day 1), Visit 3 (Treatment Day 15) and Visit 4 (Day 29, after 28 days of treatment) and a follow up phone call 5-9 days later. Three phone calls to remind subjects of dosing regimen and to inquire about adverse effects will also be done during the study and will occur between Visits 1 and 2, Visits 2 and 3, and Visits 3 and 4. The placebo-run-in is single-masked in that the subjects will remain masked to the treatment during the placebo run-in. However, the treatment is known to the investigator, medical monitor, study site personnel, and those involved in the conduct of the study. The randomized treatment assignments are double-masked in that the treatment will be masked to the investigator, medical monitor, study site personnel, subjects in the study and those involved in the conduct of the study.

This study is designed to evaluate the changes in symptoms and signs of dry eye disease including conjunctival staining of the lid wiper area of the upper eyelid (with photographs if technology is available), corneal staining, bulbar conjunctival staining, and tear break-up-time (TBUT). Dry eye symptom questionnaires including the Symptom Assessment in Dry Eye questionnaire (SANDE), the Standard Patient Evaluation of Eye Dryness (SPEED) questionnaire, and a 7-item symptom questionnaire will be completed at each visit prior to other assessments. Exploratory assessments of expression of biomarkers of inflammation in the tears and from impression cytology samples collected from the lid wiper and the bulbar conjunctiva will be performed.

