4.2. SAFETY POPULATION

The Safety Population will include all subjects who receive at least one dose of double-masked study medication in either eye. All safety analyses for the double-masked portion of the study will be conducted on the Safety Population, analyzed as treated.

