4.3. RUN-IN POPULATION

The Run-in Population will include all subjects who receive at least one dose of single-masked placebo in either eye during the run-in period. Safety analyses for the single-masked portion of the study will be conducted on the Run-in Population.

5. STATISTICAL METHODS

Descriptive statistical methods will be used to summarize the data from this study. Unless stated otherwise, the term "descriptive statistics" refers to number of subjects (n), mean, median, standard deviation (SD), minimum and maximum for continuous data and frequencies and percentages for categorical data. All data collected during the study will be included in data listings. Unless otherwise noted, the data will be sorted first by treatment group, subject number, and then by date within each subject number.

The term 'treatment group' refers to all subjects on the same dosing regimen. There will be 2 treatment groups in this study: 0.017% P-321 Ophthalmic Solution and placebo.

All statistical testing will be two-sided and will be performed using a significance (alpha) level of 0.05 unless otherwise stated.

The statistical analyses will be conducted with the SAS® System version 9.4 or higher. All analyses will be subject to formal verification procedures. Specifically, results will be verified utilizing

CONFIDENTIAL Page 14 08 August 2017

independent programming prior to issuance of the draft statistical report. All documents will be verified by the lead statistician to ensure accuracy and consistency of analyses.

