5.3.1. Adverse Events

Adverse events will be mapped to a Medical Dictionary for Regulatory Activities (MedDRA) version 19.1 preferred term and system organ classification. If a subject experiences multiple events that map to a single preferred term, the greatest severity grade and strongest investigator assessment of relation to study medication will be assigned to the preferred term for the appropriate summaries. Should an event have a missing severity or relationship, it will be classified as having the highest severity and/or strongest relationship to study medication. Summaries of incidence rates (frequencies and percentages) of individual AEs by MedDRA system organ class and preferred term will be prepared. Such summaries will be displayed for all TEAEs, TEAEs by maximum severity, and TEAEs by strongest relationship to study drug. Serious AEs and AEs leading to discontinuation of study drug will also be summarized. Separate summaries will be performed for those AEs occurring during the placebo run-in period.

All adverse events reported will be listed for individual subjects showing both verbatim and preferred terms. AEs will be flagged by run-in or double-masked treatment period as appropriate.

Any adverse event with a missing onset date will be considered to be a TEAE occurring during the double-masked treatment period.

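### SAP Table 14.3.1.5.2 puts run-in discontinuations due to adverse events on the Safety Population, which cannot include anyone who stopped drug during the run-in

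*SAP*

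**What the plan says.** SAP 4.2 defines the population for double-masked safety: "The Safety Population will include all subjects who receive at least one dose of double-masked study medication in either eye". SAP 4.3 defines the Run-in Population as "all subjects who receive at least one dose of single-masked placebo in either eye during the run-in period" and states its use: "Safety analyses for the single-masked portion of the study will be conducted on the Run-in Population". SAP 5.3 and Protocol 11.5 both call for safety analyses on each of the two populations.

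SAP Section 10 lists five pairs of adverse event tables, one of each pair for the double-masked period and one for the run-in. The run-in tables 14.3.1.1.2, 14.3.1.2.2, 14.3.1.3.2 and 14.3.1.4.2 are assigned to the Run-in Population. The fifth, 14.3.1.5.2 (events leading to discontinuation of study drug), is assigned to the "Safety Population". Apart from a hyphen, its title ends in the same words as that of 14.3.1.3.2: "Drug by System Organ Classification and Preferred Term - Placebo Run in Period".

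Two neighbouring items bear on the same split between periods:

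- SAP 5.3.1 has a rule for undated events: "Any adverse event with a missing onset date will be considered to be a TEAE occurring during the double-masked treatment period". SAP 3.3.7 has a matching sentence in its definition of double-masked treatment-emergent events.
- Tables 14.3.7.x.1 and 14.3.7.x.2 carry the same title, "Summary of Biomicroscopy and Eye Examination Data (Safety Population", with no indication of how they differ.

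**The concern.** The population label in a table title tells the programmer whom to count. Here the label selects subjects who went on to double-masked treatment, while the table is meant to describe people who stopped before it. If programmed as labelled, the table would show no discontinuation of run-in vehicle due to an adverse event, however many occurred.

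Discontinuation due to adverse events is a summary that both Protocol 11.5 and SAP 5.3.1 promise. The run-in is the only exposure of subjects who are never randomized, so this is the one summary table meant to show which events stopped drug in that group.

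The missing-onset rule has a similar weakness. It places an undated event in the double-masked period even when the subject never entered that period.

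**Working it through.** No power or sample size figure is involved. The check sets the SAP's definitions side by side.

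**Discontinuation table**

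1. Membership of the Safety Population requires at least one double-masked dose (SAP 4.2).
2. Double-masked assignment comes after the run-in: "At the end of the run-in period, eligible subjects will be randomly assigned in a double-masked fashion" (SAP 1.1). Subjects who do not qualify at Visit 2 are screen failures and are withdrawn (Protocol 7.3).
3. Take discontinuation to mean permanent withdrawal of study drug, as Protocol Appendix II distinguishes it from interruption. A subject who discontinued in the run-in then has no double-masked dose.
4. So the overlap between run-in discontinuers and the Safety Population is 0 subjects.

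**Size**

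Let R be the number who take run-in vehicle. The documents do not state it. About 125 are screened and about 65 randomized (SAP 1.1). Assume that all 65 receive a double-masked dose and that R lies between 65 and 125.

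- Run-in-only subjects = R − 65, which runs from 65 − 65 = 0 to 125 − 65 = 60.
- If k of them stop because of an adverse event, k lies between 0 and R − 65, so it is at most about 60.
- As labelled, the table counts 0 of these k. On the Run-in Population it counts k out of R.

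The 60 is a ceiling. It includes subjects who fail at Visit 1 before any drop is given, and these belong to neither population. Protocol 16.3 separates them from subjects who fail after entering the run-in.

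**Missing onset date**

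1. SAP 3.3.5 imputes incomplete run-in dates from Day -14, but it defines an incomplete date as one with at least one field known. A wholly unknown date is not covered.
2. The SAP 5.3.1 rule then assigns the event to the double-masked period.
3. For a run-in-only subject, the event leaves the run-in tables because of its assigned period, and the double-masked tables because the subject is not in the Safety Population. It remains only in the listings.
4. Such events are collected: Protocol 10.1 records events for subjects who receive run-in medication, and Protocol 16.3 collects them for run-in subjects who are not randomized.

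**Biomicroscopy**

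For BCVA (14.3.5), vital signs (14.3.6) and drop discomfort (14.3.8), the first table of the pair is on the Safety Population and the second on the Run-in Population. For biomicroscopy (14.3.7), both name the Safety Population. Biomicroscopy is done at Visits 1 and 2 (Protocol 10.4), so run-in data will exist, but no table on the list is assigned to them.

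**The case against.** The strongest reply is that this is a title slip. SAP 4.3 already gives the right population, four sibling tables follow it, Section 10 is headed as a proposed list, and a careful programmer would probably notice. The events also stay visible. Run-in treatment-emergent events are counted in 14.3.1.1.2 and 14.3.1.2.2, and serious ones in 14.3.1.4.2. Disposition Table 14.1.1 covers all enrolled subjects, and Listings 16.2.7.1 and 16.2.7.2 cover everyone. No treatment comparison or efficacy result changes. All of this stands and limits the consequence. It does not make the label harmless, because the label sets the analysis population of a named safety output, and a listing does not correct a summary table that shows none.

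Three stronger readings are tempting, and the documents do not support them:

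- A reader might infer that the table must be empty. SAP 3.3.7 defines run-in treatment-emergent events by onset or worsening. An event that began in the run-in, continued past randomization and then stopped double-masked drug could be programmed into it. What is certain is that nobody who stopped during the run-in can appear.
- A reader might infer that about 60 subjects are left out. That is only the upper limit derived above.
- A reader might infer that 14.3.7.x.2 is a mislabelled run-in table. SAP 5.3.4 asks for biomicroscopy by eye and for shifts from baseline, so the pair could be right eye and left eye, or summary and shift, both properly on the Safety Population. Relabelling the second without checking could remove a required table.

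The missing-onset gap will rarely arise, since it needs a wholly unknown date in a subject who was never randomized. The rule still fails for that case as written.

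**Conclusion.** The point holds as an internal contradiction with a specific consequence. As labelled, Table 14.3.1.5.2 conflicts with SAP 4.3 and its four sibling tables, and cannot count any subject who stopped study drug during the run-in. The number affected is unknown, from 0 to at most about 60, given that the number entering the run-in is not stated and that discontinuation means permanent withdrawal. The fault is confined to one summary table of a single-arm vehicle period.

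The missing-onset rule has a real but rare gap for run-in-only subjects. For biomicroscopy, the documents support two statements only: the purpose of the two identically titled tables is unclear, and no run-in table is identified although SAP 5.3 calls for safety analyses on both populations.

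**What to change.** 1. Change the population of Table 14.3.1.5.2 to the Run-in Population.
2. In SAP 5.3.1, and in the matching sentence in 3.3.7, limit the missing-onset rule to subjects who received double-masked drug. Assign an event with a wholly missing onset date in a run-in-only subject to the run-in period.
3. State what Tables 14.3.7.x.1 and 14.3.7.x.2 are. If the second is meant as the run-in table, relabel it to the Run-in Population. If the pair is right eye and left eye, or summary and shift, keep both and add a biomicroscopy table on the Run-in Population.

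The cost is one relabelled title, one clause stated in two places, and one relabelled or added table. No new data are needed.
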